3.3 Subject enrolment and randomisation

The Principal Investigator (PI) will ensure:

1. Signed informed consent is obtained from each potential subject before any study specific procedures are performed.
2. The eligibility of each subject is determined see Sections 3.1 and 3.2.
3. Each potential subject is assigned a unique enrolment number, beginning with "E".
4. Each eligible subject is assigned a unique randomisation code.

Randomisation will be performed before the first dose treatment at Visit 4.

Randomisation codes will be assigned strictly sequentially as subjects become eligible for randomisation.

If a subject withdraws his participation in the study, then his/her enrolment/randomisation code cannot be reused.

3.4 Procedures for handling incorrectly enrolled or randomised subjects

Subjects who fail to meet the eligibility criteria should not, under any circumstances, be enrolled or receive study medication. There can be no exceptions to this rule. Subjects who are enrolled, but subsequently found not to meet all the eligibility criteria must not be randomised or initiated on treatment, and must be withdrawn from the study.

Where a subject does not meet all the eligibility criteria but is randomised in error, or incorrectly started on treatment, the Investigators should inform the AstraZeneca Study Team Physician immediately, and a discussion should occur between the AstraZeneca Study Team Physician and the investigators regarding whether to continue or discontinue the patient from

treatment. The AstraZeneca Study Team Physician must ensure all decisions are appropriately documented.

3.5 Methods for assigning treatment groups

Patients will be randomised to placebo, AZD0585 2g and AZD0585 4 g with the ratio of 1:2:2.

Randomisation will be stratified by concomitant statin use (yes / no) at baseline and baseline TG value (<300, ≥300 mg/dL).

Stratified randomisation will be conducted so that approximately 50% or more of total randomised patients are statin users.

3.6 Methods for ensuring blinding

The treatment allocation in this study will be double-blind. To ensure the blinding of the treatments, matching AZD0585 placebo capsules will be used. Each pack will be labelled with a unique kit ID number that will be used to assign the treatment to the patient but will not indicate treatment allocation to the investigators or patient.

An un-blinded interim report will be provided based on Visit 11 data, in order to submit Japan New Drug Application. Investigators and patients will be kept blinded to randomized treatment up-to study closure.

The plasma fatty acids profile (EPA, DHA, AA and EPA/AA ratio) data from Visit4 or later and the serum TG values between Visit4 and Visit8 will also be kept double-blinded until the interim database lock. These data will not be disclosed to Investigators and patients up-to study closure.

3.7 Methods for unblinding

Individual treatment codes, indicating the treatment randomisation for each randomised subject, will be available to the Investigator(s) or pharmacists from the interactive voice response system (IVRS) / interactive web response system (IWRS). Routines for this will be described in the IVRS/IWRS user manual that will be provided to each site.

The treatment code should not be broken except in medical emergencies when the appropriate management of the subject requires knowledge of the treatment randomisation. The Investigators documents and reports the action to AstraZeneca, without revealing the treatment given to subject to the AstraZeneca representative.

AstraZeneca representatives who are independent to the study evaluation at the Patient Safety Department retains the right to break the code for serious adverse event (SAE) that are unexpected and are suspected to be causally related to an investigational product and that potentially require expedited reporting to regulatory authorities. Treatment codes will not be broken for the planned analyses of data until all decisions on the evaluability of the data from each individual subject have been made and documented.

3.8 Restrictions

Subjects will be instructed as follows for a specified period during the study:

1. Any new prescription medications or OTC preparations, supplements must be reported to study site staff during study period.
2. Continue existing therapy (if applicable) with antihypertensive agents at current dosages unless needed by the Investigators discretion during study period.
3. Fast overnight for at least 8 hours prior to each study visit, i.e., no food or beverage except water.
4. Withhold alcohol and refrain from intense exercise 24 hours prior to each study visit.
5. Do not donate blood for the duration of the study.
6. Statin dose should not be changed up to Visit 8 unless needed for safety reason at investigators discretion. Do not take lipid lowering drug except for statin up to Visit 8. Thereafter any lipid lowering drugs and/or supplements are allowed except for omega-3.
7. Subjects should not take investigational products on the morning of the study visit. Subjects bring study drug to each study visit and take investigational products just after the nearest meal after study procedure of the study visit.
8. Subjects must make every attempt to adhere to the dietary and physical activity changes and goals as discussed with the Investigator(s) during study period.
9. Women of child-bearing potential must immediately contact the Investigators if they suspect they might be pregnant and if they have changed, or plan to change their birth control method during study period.

The sponsor or designee should be contacted if the investigator is informed of any restriction violations. The sponsor will decide whether a subject with restriction violations will be allowed to continue study participation.

3.9 Discontinuation of investigational product

Subjects may be discontinued from investigational product in the following situations:

- Subject decision. The subject is at any time free to discontinue treatment, without prejudice to further treatment
- AE
- Severe non-compliance with the study protocol, as judged by the investigator(s) or AstraZeneca

3.9.1 Procedures for discontinuation of a subject from investigational product

At any time, subjects are free to discontinue investigational product or withdraw from the study (i.e., investigational product and assessments – see Section 3.10), without prejudice to further treatment. A subject that decides to discontinue investigational product will always be asked about the reason(s) and the presence of any AEs. If possible, they will be seen and assessed by an Investigator(s). AEs will be followed up (see Section 6); diary cards and all study drugs should be returned by the subject. If the patient discontinues the study during the treatment period (by Visit 18), the test and evaluations planned at Visit 18 should be performed unless the patient refuses the procedure.

If a subject is withdrawn from study, see Section 3.10.

3.10 Criteria for withdrawal

Subjects may be withdrawn from the study in the following situations:

- Subject decision. The subject is at any time free to withdraw from study
- AE
- Severe non-compliance with the study protocol, as judged by the investigator(s) or AstraZeneca
- Incorrect enrolment of the patient
- Patient falls into exclusion criteria, e.g., pregnancy
- Death
- Patient lost to follow up

3.10.1 Screen failures

Screening failures are patients who do not fulfil the eligibility criteria for the study, and therefore must not be randomised. These patients should have the reason for study withdrawal recorded as 'Incorrect Enrolment' (i.e., patient does not meet the required inclusion/exclusion criteria). This reason for study withdrawal is only valid for screen failures (not randomised patients).

3.10.2 Withdrawal of the informed consent

Patients are free to withdraw from the study at any time (investigational product and assessments), without prejudice to further treatment.

A patient who withdraws consent will always be asked about the reason(s) and the presence of any AE. The Investigators will follow up AEs outside of the clinical study.

If a subject withdraws from participation in the study, then his/her enrolment/randomisation code cannot be reused. Withdrawn subjects will not be replaced.

If possible, they will be seen and assessed by investigators. Unresolved AEs will be followed up (see Sections 6.3.2); investigational products should be returned by the subject.

3.11 Discontinuation of the study

AstraZeneca may terminate the entire study prematurely if concerns for safety arise within this study or in any other study with AZD0585.

4. STUDY PLAN AND TIMING OF PROCEDURES

Table 1 Study Plan

	Screening period				Treatment period													Withdrawal visit ^a				
	-8	-4	-2		0	4	8	10	12	16	20	24	28	32	36	40	44		48	52		
Week	1	2	3	3 ^a	4 ^c	5	6	7	8	9	10	11	12	13	14	15	16	17	18	19		
Visit window (days)	± 3	± 3	± 2		0	± 2	± 2	± 2	± 2	± 7	± 7	± 7	± 7	± 7	± 7	± 7	± 7	± 7	± 7	± 7		
Informed Consent	X																					
Eligibility Review	←				→																	
Randomisation					X																	
Demography	X																					
Medical History/Surgical History, Prior Medications	←				→																	
Brief Physical Findings ^d	X								X													X
Clinical Assessments ^e	X				X	X	X	X	X	X	X	X	X	X	X	X	X	X	X	X	X	X
Vital Sign	X				X	X	X		X	X	X	X	X	X	X	X	X	X	X	X	X	X
Fasting Lipid Panel (TG, TC, LDL-C, HDL-C, non-HDL-C, VLDL-C)	X	X	X	X	X	X	X	X	X	X	X	X	X	X	X	X	X	X	X	X	X	X
Fasting special lipid markers (RLP-C, Apo B and Apo B48)	X				X				X			X										X
Fatty acids profile (EPA, DHA, AA, and EPA/AA ratio)	X				X				X			X										X
Small dense LDL					X				X			X										X

Table 1 Study Plan

	Screening period				Treatment period														With- drawal visit ^a	
	-8	-4	-2		0	4	8	10	12	16	20	24	28	32	36	40	44	48		52
Week	1	2	3	3 ^a	4 ^c	5	6	7	8	9	10	11	12	13	14	15	16	17	18	19
Visit window (days)	± 3	± 3	± 2		0	± 2	± 2	± 2	± 2	± 7	± 7	± 7	± 7	± 7	± 7	± 7	± 7	± 7	± 7	
Apo except Apo B (A-I, A-II, C-II, C-III and E)					X				X			X			X				X	
hs-CRP					X				X			X			X				X	
Fasting special lipid markers (Lp(a), PCSK9)					X				X			X			X				X	
Clinical Chemistry	X	X			X	X			X	X		X			X				X	
Haematology	X	X			X	X			X	X		X			X				X	
Thromboplastin time (PT), Partial thromboplastin time (PTT)		X			X				X			X			X				X	
Urinalysis	X	X			X	X			X	X		X			X				X	
HbA1c	X				X				X			X			X				X	
Assessment of renal function (Estimated glomerular filtration rate [eGFR], Albumin Creatinine Ratio [ACR])	X																			
TSH	X																			
Urine Pregnancy Test	X				X														X	

Table 1 Study Plan

Week	Screening period				Treatment period														Withdrawal visit ^a			
	-8	-4	-2		0	4	8	10	12	16	20	24	28	32	36	40	44	48		52		
Visit	1	2	3	3a ^b	4 ^c	5	6	7	8	9	10	11	12	13	14	15	16	17	18	19		
Visit window (days)	± 3	± 3	± 2		0	± 2	± 2	± 2	± 2	± 7	± 7	± 7	± 7	± 7	± 7	± 7	± 7	± 7	± 7	± 7		
ECG	X				X				X			X			X					X		
Diet Counselling on Therapeutic Lifestyle Changes (TLC) diet	X	X	X		X	X	X	X	X	X	X	X	X	X	X	X	X	X	X			
Question Adherence to TLC diet		X			X	X	X	X	X	X	X	X	X	X	X	X	X	X	X		X	
Dispense Investigational Product					X	X	X		X	X	X	X	X	X	X	X	X	X	X			
Assess Investigational Product Compliance						X	X		X	X	X	X	X	X	X	X	X	X	X		X	
AEs/SAEs ^f	←																				→	
Concomitant and other treatments	←																					→

^a If a patient withdraws before completion of 52 weeks of treatment, withdrawal visit should be carried out to evaluate the patient's safety.

^b If the investigators decide that an additional test is appropriate, Visit 3a is allowed. See section 3.1, 2nd inclusion criterion for details.

^c All examinations to be completed before randomisation.

^d Brief physical findings consisting of an evaluation of general appearance, respiratory, cardiovascular, abdomen, skin, head and neck (including ears, eyes, nose and throat), lymph nodes, thyroid, musculo-skeletal (including spine and extremities) and neurological systems.

^e Clinical assessments: Subjects will be questioned regarding the occurrence and nature of any symptoms and signs. Weight will be measured at each time; however, height will be measured only at Visit 1 to determine the body mass index (BMI).

^f SAEs will be recorded from the time of informed consent (Visit 1), and non-serious AEs will be collected from time of randomisation (Visit 4).

4.1 Screening period

Investigator(s) should keep a record, the subject screening log, of subjects who entered pre-study screening. Investigators will obtain signed informed consent from a potential subject before starting screening period. Each subject should meet all of the inclusion criteria and none of the exclusion criteria for this study. Under no circumstances can there be exceptions to this rule.

Screening period takes 8 weeks. Concomitant medications for hyperlipidemia except for statins are not allowed to use.

Subjects will take 3 study visits during screening period (Visit 1, Visit 2 and Visit 3). TG, LDL-C and other laboratory data will be measured at each visit, then only the subjects with TG and LDL-C values within acceptable ranges of variability will be randomised (see Sections 3.1). In case repeat of Visit 3 test (Visit 3a) is performed between Visit 3 and 4 at investigators discretion, eligibility should be re-evaluated with using Visit 3a data (see Section 3.1).

The following assessments and procedures should be performed during screening period as per Table 1.

- Demography (date of birth, sex, race and ethnicity)
- Medical history/Surgical history and prior medications
- Brief physical findings
- Clinical assessments (occurrence and nature of any symptoms and signs, body weight, height)
- Vital signs (BP and pulse)
- Clinical Chemistry/Haematology/Urinalysis
- ECG
- Urine pregnancy test for women of childbearing potential
- Diet counselling on TLC diet/Question adherence to TLC diet
- AEs must be captured from time of consent. However, screening period of the study only SAEs will be collected.
- Concomitant and other treatments

The investigators should adhere to the study plan, procedures and perform tests/observations in accordance with the protocol.

4.2 Treatment period

The following assessments and procedures should be performed during treatment period as per Table 1.

- Brief physical findings

- Clinical assessments (occurrence and nature of any symptoms and signs, body weight)
- Vital signs (BP and pulse)
- Clinical Chemistry/Haematology/Urinalysis
- ECG
- Urine pregnancy test for women of childbearing potential
- Diet counselling on TLC diet/Question adherence to TLC diet
- Dispense investigational product
- Assess investigational product compliance
- AEs
- Concomitant and other treatments

The Investigators should adhere to the study plan, procedures and perform tests/observations in accordance with the protocol.

4.3 Withdrawal visit

The following assessments and procedures should be performed if subjects withdraw from the study before they complete 52 weeks treatment, i.e., Visit 18 (see [Table 1](#)).

- Brief physical findings
- Clinical assessment (occurrence and nature of any symptoms and signs, body weight)
- Vital signs (BP and pulse)
- Clinical Chemistry/Haematology/Urinalysis
- Urine pregnancy test for women of childbearing potential
- ECG
- Question adherence to TLC diet
- Assess investigational product compliance
- AEs
- Concomitant and other treatments

The Investigators should adhere to the study plan, procedures and perform tests/observations in accordance with the protocol.

5. STUDY ASSESSMENTS

The Rave Web Based Data Capture (WBDC) system will be used for data collection and query handling.

The investigators will ensure that data are recorded on the Electronic Case Report Form (eCRF) as specified in the study protocol and in accordance with the instructions provided.

The PI ensures the accuracy, completeness, and timeliness of the data recorded and of the provision of answers to data queries according to the Clinical Study Agreement (CSA). The PI will sign the completed eCRF. A copy of the completed eCRF will be archived at the study site.

5.1 Efficacy assessments

Blood samples will be taken at the times indicated in the Study Plan (see [Table 1](#)).

The samples are measured by SRL Medisearch Inc. The detailed procedure of sampling, handling and shipping is described in the standard operating procedure made by AstraZeneca.

The valuables for efficacy assessment are as follows;

- Fasting serum TG
- Fasting serum lipid profile: TC, LDL-C*, VLDL-C, HDL-C and non-HDL-C* (*direct method)
- Apolipoprotein: Apo A-I, Apo A-II, Apo B, Apo B48, Apo C-II, Apo C-III, and Apo E
- Plasma fatty acids profile: EPA, DHA, AA, and EPA/AA ratio
- Small dense LDL and LDL-C/Apo B ratio
- Lp(a), RLP-C, PCSK9 and hs-CRP

The plasma fatty acids profile (EPA, DHA, AA and EPA/AA ratio) data from Visit 4 or later and the serum TG values between Visit 4 and Visit 8 must not be disclosed to Investigators and patients until the study closure.

In addition, the plasma fatty acids profile data from Visit 4 or later and the serum TG values between Visit 4 and Visit 8 will be kept double-blinded until the interim database lock.

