5.2 Safety assessments

5.2.1 Laboratory safety assessments

Blood and urine samples for determination of clinical chemistry, haematology, coagulation, and urinalysis will be taken at the times indicated in the Study Plan (see [Table 1](#)).

Blood samples will be measured by SRL Medisearch Inc.

The detailed procedure of sampling, handling and shipping is described in the standard operating procedure made by AstraZeneca. In addition, the PI ensures that samples are labelled and shipped in accordance with the Laboratory Manual and the Biological Substance, Category B Regulations (materials containing or suspected to contain infectious substances

that do not meet Category A criteria), see Appendix C ‘International Airline Transportation Association (IATA) 6.2 Guidance Document’. Any samples identified as Infectious Category A materials are not shipped and no further samples will be taken from the subject unless agreed with AstraZeneca and appropriate labelling, shipment and containment provisions are approved.

Urinalysis will be performed at each study site by dipstick provided by SRL Medisearch Inc.

The following laboratory variables will be measured:

Table 2 Laboratory Safety Variables

Haematology/Haemostasis	Clinical Chemistry
B-Haemoglobin (Hb)	S-Creatinine
B-Leukocyte count	S-Bilirubin, total
B-Leukocyte differential count (absolute count)	S-Alkaline phosphatase (AP)
B-Platelet count	S-AST
B-Haematocrit	S-ALT
P-PT	S-Albumin
P-PTT	S-Potassium
Urinalysis	S-Calcium, total
U-Hb	S-Sodium
U-Protein/Albumin	S-Creatine kinase (CK)
U-Glucose	S-TSH
U-Pregnancy	B-HbA1c
	P-Glucose
	S-LDL-C
	S-Apo B

The Investigator should make an assessment of the available results with regard to clinically relevant abnormalities. The laboratory results should be signed and dated and retained at site as source data for laboratory variables. For information on how AEs based on laboratory tests should be recorded and reported, see Section 6.3.

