6.3.6 Adverse events based on examinations and tests

The results from protocol mandated laboratory tests, vital signs, ECGs and other safety assessments will be summarised in the clinical study report. Deterioration as compared to baseline in protocol-mandated laboratory values, vital signs, ECGs and other safety assessments should therefore only be reported as AEs if they fulfil any of the SAE criteria or are the reason for discontinuation of treatment with the investigational product.

If deterioration in a laboratory value or vital sign is associated with clinical signs and symptoms, the sign or symptom will be reported as an AE and the associated laboratory result or vital sign will be considered as additional information. Wherever possible the reporting investigator uses the clinical, rather than the laboratory term (e.g., anaemia versus low Hb value). In the absence of clinical signs or symptoms, clinically relevant deteriorations in non-mandated parameters should be reported as AE(s).

Any new or aggravated clinically relevant abnormal medical finding at a physical examination as compared with the baseline assessment will be reported as an AE.

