6.7 Management of investigational product related toxicities (Not Applicable)

6.8 Study governance and oversight

6.8.1 Steering Committee

A Steering Committee will be set up in this clinical study. The Steering Committee charter will be prepared to detail responsibilities. The Steering Committee constitutions are presented in Supplement A.

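### Serum TG from Visit 4 to Visit 8 is withheld from sites until study closure with no safety exception, and neither document states an alert for an extreme value (low-priority safety gap)

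*Protocol*

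**What the plan says.** The masking rule appears twice. Section 5.1 says that "the serum TG values between Visit 4 and Visit 8 must not be disclosed to Investigators and patients until the study closure". Section 3.6 also withholds the values from investigators and patients up to study closure, and adds that "the serum TG values between Visit4 and Visit8 will also be kept double-blinded until the interim database lock". Neither section has a safety exception.

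Other restrictions do have one:

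- Treatment code (section 3.7): "The treatment code should not be broken except in medical emergencies when the appropriate management of the subject requires knowledge of the treatment randomisation".
- Statin dose (section 3.8): "Statin dose should not be changed up to Visit 8 unless needed for safety reason at investigators discretion".

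Section 5.2.1 sets the site's laboratory review: "The Investigator should make an assessment of the available results with regard to clinically relevant abnormalities". Table 2 there lists LDL-C and Apo B as safety variables but not TG. Under section 6.3.6, worsening of protocol-mandated laboratory values "should therefore only be reported as AEs if they fulfil any of the SAE criteria or are the reason for discontinuation of treatment" with the study drug. On oversight, section 6.8.1 says "A Steering Committee will be set up in this clinical study"; its charter was not supplied.

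**The concern.** TG is the condition under treatment, and section 1.3 links it to pancreatitis and cardiovascular risk. Masking it during the efficacy period is sensible, because a patient's TG response hints at the arm. But if TG rose sharply in the first 12 weeks, the laboratory would hold the result, and anyone following the two documents exactly would not pass it on. The site cannot assess a result it does not have. A value nobody at the site has seen cannot be the reason for stopping treatment, so it would not become an adverse event by that route either. What is at stake is the safety of an occasional patient, not the efficacy comparison.

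**Working it through.** **1. Is there an alert rule elsewhere?**

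- Section 3.9 opens its list with "Subjects may be discontinued from investigational product in the following situations". The situations are subject decision, adverse event and severe non-compliance; there is no TG criterion.
- Section 3.10 (withdrawal) has no TG criterion.
- Section 6.7 (toxicity management) is marked not applicable.
- SAP section 4.2.3 has threshold tables for liver enzymes and QTcF only.
- Emergency unblinding in section 3.7 releases the treatment code, not a TG result.

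**2. How long is a value unseen?** Reading the window as inclusive, Weeks 0, 4, 8, 10 and 12 are masked. For a patient who stays in the study, the next scheduled visible TG is Week 16. Windows (Table 1) are ±2 days to Week 12 and ±7 days at Week 16, so the gap is (16 − week) × 7 ± 9 days.

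| Masked visit | Gap in days |
|---|---|
| Week 4 | 84 ± 9 = 75 to 93 |
| Week 8 | 56 ± 9 = 47 to 65 |
| Week 10 | 42 ± 9 = 33 to 51 |
| Week 12 | 28 ± 9 = 19 to 37 |

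If the end visits are excluded, Week 12 is visible and the nominal gaps from Weeks 4, 8 and 10 are 56, 28 and 14 days.

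**3. The plan's own figure.** Section 8.2 gives SD 24%, difference 12.5, 75 placebo against 150 per dose, two-sided 0.025. SE = 24 × √(1/75 + 1/150) = 3.39. Power ≈ Φ(12.5/3.39 − 2.241) = 92.5%, or 92.2% with the noncentral t. The stated 92% reproduces, so the SD and SE can be used below.

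**4. How often would an extreme value occur?** Assumptions, because the documents give no baseline distribution or visit-level SD:

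- The 24% SD belongs to the mean of two visits. The single-visit SD is 24/√((1+ρ)/2): 25.3% for ρ = 0.8 and 27.7% for ρ = 0.5.
- Typical changes m are the overseas medians in section 1.1: −4%, −15% and −21%.
- Percent change is either normal, or log-normal with median ratio 1+m and log-SD s solving (1+m)·exp(s²/2)·√(exp(s²)−1) = single-visit SD. For placebo at ρ = 0.5, s = 0.273.
- There are four on-treatment values with equal correlation ρ, simulated in 2,000,000 patients.

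Example for placebo from 450 to 1000 mg/dL, log-normal, ρ = 0.5: z = ln(1000/(450 × 0.96))/0.273 = 3.07, or 0.11% at one visit and 0.39% at any of four. The normal model gives about 0.001%.

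Chance that any of the four values reaches the level:

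| Baseline | Level (mg/dL) | Placebo | 2 g | 4 g |
|---|---|---|---|---|
| 265 | 1000 | <0.001% | <0.001% | <0.001% |
| 450 | 1000 | ≤0.39% | ≤0.30% | ≤0.27% |
| 490 | 1000 | ≤1.0% | ≤0.72% | ≤0.63% |
| 450 | 700 | 2.3–11.5% | 0.7–7.4% | 0.35–5.9% |
| 450 | 500 | 44–59% | 27–43% | 20–35% |

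If all 375 patients started at 450, which is extreme, the upper count at 1000 is 75 × 0.39% + 150 × 0.30% + 150 × 0.27% = 1.1. If a tenth did, it is 0.11.

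**5. What would an alert do to the primary comparison?** Suppose rescue after an alert lowers a patient's endpoint by 50 points.

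- One placebo patient moves the placebo mean by 50/75 = 0.67 points, against an SE of 3.39.
- At 1000, with everyone starting at 450 and the upper rates, the 4 g difference shrinks by 50 × (0.39% − 0.27%) = 0.06 points.
- At 700, on the same basis, about 75 × 11.5% = 8.6 placebo patients are alerted. The differences shrink by 50 × (11.5% − 7.4%) = 2.1 points for 2 g and 50 × (11.5% − 5.9%) = 2.8 points for 4 g, out of a planned 12.5.

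**The case against.** The strongest reply is that an alert may already exist. Sections 5.1 and 5.2.1 send laboratory procedure to a sponsor operating procedure and a Laboratory Manual, neither supplied. This stands: a reader might infer that no alert process exists, and the documents do not support that. They show only that none is stated in the protocol or SAP. The wording still matters, because a rule in the manual that reported a masked TG to the site would contradict sections 3.6 and 5.1.

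The second reply is that the risk is close to nil, and much of that stands too. Section 3.1 caps mean entry TG at 499 mg/dL and requires the change between Visits 2 and 3 to be within 30%. Section 3.2 excludes:

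- a history of pancreatitis;
- lipoprotein lipase and Apo C-II deficiency and familial dysbetalipoproteinemia;
- type I diabetes, insulin use and HbA1c above 10%;
- uncontrolled hypothyroidism;
- systemic corticosteroids;
- alcohol abuse.

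The model above allows for none of these exclusions, so its upper ends are probably too high. TC, non-HDL-C and VLDL-C are scheduled at every masked visit and are not named as masked. Symptoms are asked about at every visit, and section 6.3.6 records symptoms that accompany a laboratory change as adverse events. Nothing bars a local TG test. These safeguards are indirect, though: none makes anyone responsible for acting on an extreme masked TG.

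The third reply is that an alert erodes the masking. That is right at 500 to 700 mg/dL, where alerts would be frequent from a high baseline and uneven by arm. It is not right near 1000.

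**Conclusion.** The point holds as a low-priority safety gap. The non-disclosure rule is absolute, comparable restrictions carry a safety clause, and no TG alert is stated in either document.

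The gap in time can be long (75 to 93 days from Week 4), but extreme values should be rare: at most about 0.39% of placebo patients starting at 450 mg/dL, about 1.0% at 490, and essentially none at 265. These rates rest on the planning SD, overseas median changes, an assumed visit correlation of 0.5 to 0.8 and the more cautious of two distributions. The 1000 mg/dL level is itself an assumption, not a figure from the documents.

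A reader might go further and infer a threat to the efficacy result, or a meaningful number of patients at risk. Neither is supported. The gap does not touch sample size, alpha or power, and even the count of 1.1 patients requires all 375 to start at 450.

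**What to change.** Keep the masking and add one exception to sections 3.6 and 5.1. If a masked TG is at or above a prespecified level, the central laboratory notifies the investigator and a sponsor physician independent of the study evaluation, and the notification is recorded in the eCRF. The level should be about 1000 mg/dL, to be confirmed by the sponsor's medical function, and not near 500 to 700. If the Laboratory Manual already has such a rule, refer to it and still add the exception, so that the documents agree.

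In the SAP, keep alerted patients in the FAS primary analysis and list them by arm. Do not exclude them in a sensitivity analysis, because that would select on a post-randomisation outcome.

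The cost is a short amendment, a laboratory flag and one eCRF field. The downside is a very rare disclosure of one patient's TG before Week 12, slightly more often on placebo when baseline is high, with a negligible effect on the primary comparison.
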